7.3. Adverse Events

AEs will be coded using MedDRA version 23.0. or later.

All reported AEs (whether treatment emergent or not) will be included in by-subject AE listings. Sorting will be by treatment subject, date of event, SOC, PT and then verbatim description.

An AE will be considered treatment emergent (TEAE) if it begins or worsens in severity after the first dose of the double-blind study treatment through 14 days after the last dose of study treatment. Partial AE start dates will be imputed as detailed in [Section 4.2.2](#)

Summary tables will be based on TEAEs. The incidence of TEAEs will be presented using counts and percentages of subjects with TEAEs and tabulated by SOC and PT. SOC will be sorted in descending frequency and PT within SOC will be sorted by descending frequency based on the incidence across subjects overall. If a subject has multiple occurrences (start and stop) of an event associated with a specific SOC or PT within a SOC, a subject will only be counted once in the incidence count for the SOC or PT within SOC respectively.

An overall summary table of AEs by treatment group will be presented detailing the number and percentage of subjects, and number of events for the following categories:

- At least one TEAE;
- At least one Treatment-Related TEAE;
- At least one Grade ≥ 3 TEAE (Mild = Grade 1, Moderate = Grade 2, Severe = Grade 3,

Life-Threatening = Grade 4, Death = Grade 5)

- At least one Grade ≥ 3 Treatment-Related TEAE;
- At least one Serious TEAE;
- At least one Serious Treatment-Related TEAE;
- At least one TEAE leading to Discontinuation from Study Medication;
- At least one TEAE of Special Interest;
- At least one Treatment-Related TEAE of Special Interest

Except for all TEAEs which will be summarized by SOC and PT, the incidence of all other TEAEs by PT will be presented for the following

- All TEAEs by SOC and PT;
 - Treatment-related TEAEs (i.e., possibly or probably related);
 - All TEAEs by PT, and maximum severity (where the maximum intensity per subject will be counted at each level of summarization);
- TEAES with Grade ≥ 3 ;

- Treatment-related TEAES with Grade ≥ 3 ;
- Serious TEAEs;
- Treatment-related serious TEAEs;
- Fatal TEAE;
- TEAEs leading to discontinuation from study treatment;
- TEAE of Special Interest;
- Treatment-related TEAE of Special Interest;
- Non-fatal serious TEAE;
- Hypertension TEAEs by Pre-existing Hypertension (Yes vs No) and Baseline Hypertension (Yes vs. No). Hypertension TEAEs will be selected using the same list of preferred terms as specified in [Section 5.2](#).
- All TEAEs by PT occurring in at least 2% of subjects in the vibegron arm and greater than the placebo arm will be created and sorted by descending frequency in the vibegron arm.
- Gastrointestinal/IBS-related TEAEs by PT will be prepared and sorted by descending frequency in the vibegron arm. The final list of GI/IBS-related PT will be finalized and documented prior to database lock.

Adverse events of special interest for this study include:

- Adverse events suggestive of cystitis or urinary tract infection (UTI)
- Potential major cardiac and cerebrovascular events, including all cause death, myocardial infarction, cerebrovascular accident, hospitalization for unstable angina or chest pain, hospitalization for heart failure and coronary revascularization/angioplasty/stent
- Hypertension
- AEs consistent with orthostatic hypotension as confirmed by orthostatic vital signs
- Elevated serum aspartate aminotransferase (AST) or alanine aminotransferase (ALT) lab value requiring that study drug be temporarily withheld or permanently discontinued

Overall AE listing will include the treatment arm, start and stop dates/times of the AE, first dose and last dose dates/times of double-blind treatment and days on study relative to the day of first dose and last dose of double-blind study treatment. In addition, the listing will indicate if the AE is treatment emergent (Yes vs No), an AE is of Special Interest (Yes vs No) and include the onset period (See [Section 4.2.4.1](#) for the definition of the periods).

A Treatment related AE is defined as an AE for which the investigator classifies the AE as being “Probably Related” or “Possibly Related” to study treatment on Adverse Event CRF. Missing relationship and severity (intensity) will be imputed per [Section 4.2.2](#).

The following additional listings will be provided:

- Listing of deaths
- Listing of Serious TEAEs
- Listing of treatment-emergent AESIs
- Listing of TEAEs leading to withdrawal or Interruption of study treatment

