9.4.3.1. Adverse Events

An AE will be considered a treatment-emergent AE (TEAE) if:

- The AE began on or after the date of the first dose of study drug; or
- The AE was present before the date of the first dose of study drug, but increased in severity or became serious on or after the date of the first dose of study drug

An AE that occurs more than 14 days after the last dose of study drug will not be counted as a TEAE.

An AE will be considered a treatment-emergent SAE (TESAE) if it is a TEAE that additionally meets any SAE criteria.

AEs will be coded using MedDRA version 21.1 (or later). An overall summary table of AEs by treatment group will be presented with number and percentage of subjects. The incidence of all TEAEs by primary SOC and PT will be prepared for all TEAEs, serious TEAEs, treatment -related TEAEs, treatment-related serious TEAEs, TEAEs leading to discontinuation from study drug, AESIs, and all TEAEs by maximum intensity. All AEs will be listed, with a flag designating AEs that are treatment emergent.

[figure not shown]

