14.3.2.3	Treatment-related TEAEs by Preferred Term	SAF		EOS
14.3.2.4	Treatment-Emergent Adverse Events by Preferred Term and Maximum Intensity	SAF		EOS
14.3.2.5	Treatment-Emergent Adverse Events Occurring in $\geq 2\%$ Subjects of Vibegron Arm and Greater Than the Placebo by Preferred Term	SAF		EOS
14.3.2.6	Treatment-Emergent Adverse Events with Grade ≥ 3 by Preferred Term	SAF		TL, EOS
14.3.2.7	Treatment-related TEAEs with Grade ≥ 3 by Preferred Term	SAF		EOS
14.3.2.8	Serious TEAEs by Preferred Term	SAF		EOS
14.3.2.9	Treatment-related Serious TEAEs by Preferred Term	SAF		EOS
14.3.2.10	Fatal TEAEs by Preferred Term	SAF		EOS
14.3.2.11	TEAEs Leading to Treatment Discontinuation by Preferred Term	SAF		TL, EOS
14.3.2.12	TEAEs of Special Interest by Preferred Term	SAF		EOS
14.3.2.13	Treatment-related TEAEs of Special Interest by Preferred Term	SAF		TL, EOS
14.3.2.14	Non-Fatal Serious TEAEs by Preferred Term	SAF		EOS

Title		Analysis Set	Programming Note	Deliverable
14.3.2.15	Hypertension TEAEs by Preferred Term and Pre-existing Hypertension	SAF	Search for the following terms hypertension PTs: Accelerated hypertension, Diastolic hypertension, Essential hypertension, Hypertension, Hypertensive crisis, Hypertensive emergency, Hypertensive heart disease, Malignant hypertension, Malignant hypertensive heart disease, Secondary hypertension, Supine hypertension, Systolic hypertension	EOS
14.3.2.16	Hypertension TEAEs by Preferred Term and Baseline Hypertension Status	SAF	Search for the following terms hypertension PTs: Accelerated hypertension, Diastolic hypertension, Essential hypertension, Hypertension, Hypertensive crisis, Hypertensive emergency, Hypertensive heart disease, Malignant hypertension, Malignant hypertensive heart disease, Secondary hypertension, Supine hypertension, Systolic hypertension	EOS
14.3.2.17	GI/IBS-related TEAEs by Preferred Term	SAF		EOS
14.3.2.18	List of Deaths	SAF		EOS
14.3.2.19	Listing of Treatment Emergent Serious TEAEs	SAF		EOS
14.3.2.20	Listing TEAEs Leading to Withdrawal or Interruption of Study Treatment	SAF		EOS
14.3.2.21	Listing of TEAEs of Special Interest	SAF		EOS

Title		Analysis Set	Programming Note	Deliverable
Laboratory data				
14.3.3.1	Hematology Laboratory Parameters	SAF	Include observed and CFB; include conventional units as well for hematocrit	EOS
14.3.3.2	Abnormal Classification of Hematology Laboratory Parameters	SAF		EOS

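### SAP 7.3 leaves the seriousness clause out of the protocol's TEAE definition without declaring it, and its start point conflicts with the protocol and the SAP's own period table for Day 1 onsets

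*SAP*

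**What the plan says.** Protocol 9.4.3.1 gives two ways for an AE to be treatment emergent. The first is by onset: "The AE began on or after the date of the first dose of study drug". The second covers an event present before that date which "increased in severity or became serious on or after the date of the first dose of study drug". Events more than 14 days after the last dose are excluded. A serious event must pass this test before it counts as treatment emergent: "An AE will be considered a treatment-emergent SAE (TESAE) if it is a TEAE that additionally meets any SAE criteria".

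SAP 7.3 replaces this with a single sentence: "An AE will be considered treatment emergent (TEAE) if it begins or worsens in severity after the first dose of the double-blind study treatment". The window closes 14 days past the last dose. There is no seriousness clause, and the starting point is the dose itself, not the date of the dose.

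SAP 7.3 then says: "Summary tables will be based on TEAEs". The serious-event table, 14.3.2.8, is titled "Serious TEAEs by Preferred Term". The serious listings (the one named in SAP 7.3, 14.3.2.19 and 16.2.3.2.2) are also limited to treatment-emergent events. The visible text of SAP Section 9, which records departures from the protocol, covers efficacy and exploratory analyses only. The v1.0 to v2.0 log in SAP 11.3 does not mention the TEAE definition.

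**The concern.** The protocol keeps severity and seriousness apart. Protocol 10.3 says that an event is serious because it meets an SAE criterion, not because of its severity rating. A rule that looks only for onset or a rise in severity therefore cannot be relied on to pick up every event that turns serious.

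Pre-existing events will be in the database. Protocol 8.4.1 has AEs recorded from consent, and every subject passes through a 2-week placebo run-in before randomization. If such an event turns serious on double-blind treatment at an unchanged grade, the protocol attributes it to the treatment period and the SAP does not. It is then missing from the displays a reader would use to compare serious events between arms.

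The starting point is a second, separate issue. It matters for events with onset on Day 1 and for events whose partial onset date is imputed to Day 1. It does not contribute to the omission of run-in events that turn serious later.

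**Working it through.** The plan states no figure on this point, so the check compares the rules clause by clause and runs typical cases through them.

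**Inputs**
- Protocol 9.4.3.1: onset on or after the first-dose date, or a pre-existing event that increases in severity or becomes serious from that date.
- SAP 7.3: onset or worsened severity after the first double-blind dose.
- SAP 4.2.4.1, Table 1: an AE belongs to the blinded-treatment period if its start date is on or after the date of the first double-blind dose.
- SAP 4.2.3: some partial onset dates are set to the date of the first double-blind dose.
- Protocol 10.3: the five-grade intensity scale and the seriousness criteria.

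**Reading of the protocol.** It anchors to study drug, a term that Protocol 6.1.1 also uses for run-in placebo. The table takes the anchor to be the first double-blind dose. Read literally, a run-in event would already be a TEAE by onset. In case 1 the protocol therefore counts the event on either reading.

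**Is the event a TEAE?** The SAP rule is applied by clock time and by date alone. The last column shows whether Table 1 places the onset in the blinded-treatment period.

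| Case | Protocol | SAP 7.3, clock time | SAP 7.3, date only | Table 1 |
|---|---|---|---|---|
| 1. Run-in onset, becomes serious on treatment, same grade | Yes | No | No | No |
| 2. Run-in onset, becomes serious, grade rises | Yes | Yes | Yes | No |
| 3. Run-in onset, grade rises, not serious | Yes | Yes | Yes | No |
| 4. Day 1 onset after the dose | Yes | Yes | No | Yes |
| 5. Day 1 onset before the dose | Yes | No | No | Yes |
| 6. Onset imputed to Day 1, no time | Yes | No | No | Yes |
| 7. Day 2 onset | Yes | Yes | Yes | Yes |

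Case 1 isolates the missing seriousness clause. Cases 2 and 3 show that a rise in grade is enough to bring the event back in. Cases 4 to 6 isolate the starting point. In cases 5 and 6, and in case 4 if only dates are compared, the overall AE listing could show one event with a blinded-treatment onset period and a TEAE flag of No, because SAP 7.3 puts both items in that listing.

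**How wide is case 1?** Protocol 10.3 gives six kinds of seriousness: death, threat to life, hospitalization, disability, congenital anomaly, and other medically important events. Four of them have counterparts in the intensity scale. Grade 3 refers to hospitalization and to disabling events, Grade 4 to life-threatening events, and Grade 5 is death. A Grade 1 or 2 run-in event that becomes serious on one of these four would normally rise in grade and be kept. Two main groups remain:
- events already at Grade 3 before double-blind dosing;
- events made serious by medical judgement, or by a rule not based on intensity. Protocol 8.4.7.1, for example, makes one class of liver-enzyme elevation an SAE through its persistence.

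**The case against.** The strongest reply is that the gap is close to empty. The intensity scale overlaps with most seriousness criteria, and clinical status is rechecked at Visit 3, so few women should start double-blind treatment with an ongoing Grade 3 event. This stands, and it is why the point is minor.

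An exacerbation can itself qualify as an AE under Protocol 10.3. If entered as a new record, its onset would fall on treatment and the SAP would count it. This stands only in part, because Protocol 8.4.3 sends updated information to the original eCRF record.

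A reader might infer that on-treatment SAEs would vanish from the trial's reporting. The documents do not support that. SAP 7.3 puts every AE, treatment emergent or not, in the by-subject listings with its onset period, and there is a separate deaths listing. SAE reporting within 24 hours does not depend on TEAE status, and the DSMB's remit covers all SAEs. The safety analysis is descriptive, so no test result changes.

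A reader might also infer that both wording differences cause the serious-event omission. They do not: the starting point affects only Day 1 and imputed onsets. There, the time of the witnessed first dose is recorded and the AE listing carries times. Applying the SAP rule by the clock is therefore workable where times exist, and leaving out an event that began before the Day 1 dose is defensible in itself. It still departs from the protocol and from Table 1, and an imputed date has no time to compare.

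Finally, Protocol 9.4.3 leaves full definition of the safety analysis to the SAP, and the SAP's explicit double-blind anchor is clearer than the protocol's term. Both points are fair. Neither explains why a stated clause was removed without being recorded as a change.

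**Conclusion.** The point holds in a limited form. SAP 7.3 narrows the protocol's TEAE definition without declaring it, and one identifiable type of event falls through: an AE present before double-blind treatment that becomes serious during it at an unchanged grade. That event would be missing from the TEAE tables, the serious TEAE tables and the serious listings. It would be visible only in the overall AE listing, marked as not treatment emergent; a death would also be in the deaths listing.

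Few or no such events are expected. The documents give no rate of events that turn serious without a grade change, so no percentage can be attached, and none should be inferred from the arm sizes. The conclusion assumes that SAP 7.3 is programmed as written and that the event stays in its original record.

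The Day 1 conflict is a separate inconsistency between SAP 7.3 on one side and Protocol 9.4.3.1 and SAP Table 1 on the other. It concerns classification and loses no data.

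**What to change.** Reword the TEAE sentence in SAP 7.3 so that an AE is treatment emergent if it begins, or worsens in severity or becomes serious, on or after the date of the first double-blind dose through 14 days after the last dose. This restores the protocol's clause, keeps the SAP's clearer double-blind anchor and agrees with Table 1 in Section 4.2.4.1. Under this wording all seven cases above are classified as in the protocol. If the narrower rule is intended, record and justify it in SAP Section 9.

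In the same edit, correct the cross-reference for partial AE dates: SAP 7.3 points to Section 4.2.2, but the imputation rules are in 4.2.3.

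The cost is one SAP sentence and the matching line in the TEAE derivation. No new data are needed.

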2.3.2. Potential Risks

To date, in subjects (male or female) with overactive bladder, no adverse reactions specific to vibegron have been identified.

Based on aggregate preclinical, clinical pharmacology, and Phase 2 and 3 studies, AEs of special interest (AESIs) predefined for specific evaluations in vibegron clinical studies are as follows:

[figure not shown]
- Potential major cardiovascular events
- Hypertension
- AEs suggestive of orthostatic hypotension
- AEs suggestive of cystitis or urinary tract infection
- Elevated AST or ALT lab value requiring that the study drug be temporarily withheld or permanently discontinued

Prespecified definitions of AESIs are provided in [Section 8.4.7](#). More detailed information about the known and expected benefits and risks and reasonably expected AEs of vibegron may be found in the most recent version of the Investigator's Brochure.

3. Objectives and Endpoints

Objectives	Endpoints
Primary	
To compare the effect of vibegron vs placebo in subjects with abdominal pain due to IBS-D on the API weekly responder rate over 12 weeks
 
 • Proportion of IBS-D subjects who are API weekly responders over 12 weeks 
 - An API Weekly Responder is defined as a subject who experiences a decrease in the weekly average of “worst abdominal pain in the past 24 hours” scores of at least 30% compared with the baseline weekly average
Secondary	
To compare the effect of vibegron vs placebo in subjects with abdominal pain due to IBS-D or IBS-M on patient-reported outcomes
 
 • Proportion of GIS responders at Week 12 for all IBS subjects, including IBS-D and IBS-M subjects

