^f If total bilirubin is elevated above the upper limit of normal.

^g Only upon request from Principal Investigator (if ALT, AST and bilirubin are increased).

10.3. Appendix 3: Adverse Events: Definitions and Procedures for Recording, Evaluating, Follow-up, and Reporting

Definition of AE

AE Definition

An AE is any untoward medical occurrence in a clinical study subject, temporally associated with the use of study drug, whether or not considered related to the study drug.

An AE can therefore be any unfavorable and unintended sign (including an abnormal laboratory finding), symptom, or disease (new or exacerbated) temporally associated with the use of study drug.

AE of Special Interest

An AESI (serious or nonserious) is one of scientific and medical concern specific to the Sponsor's study drug or program, which warrants ongoing monitoring and rapid communication by the Investigator to the Sponsor or designee. Such an event might warrant further investigation in order to characterize and understand it. See [Section 8.4.7](#) for AESIs defined for this study.

Events Meeting the AE Definition

- Any abnormal laboratory test results (hematology, clinical chemistry, or urinalysis) or other safety assessments (eg, ECGs, radiological scans, vital signs measurements), including those that worsen from baseline, considered clinically significant in the medical and scientific judgment of the Investigator (ie, not related to progression of underlying disease)
- Exacerbation of a chronic or intermittent pre-existing condition including either an increase in frequency and/or intensity of the condition
- New condition detected or diagnosed after study drug administration even though it may have been present before the start of the study
- Signs, symptoms, or the clinical sequelae of a suspected drug-drug interaction
- Signs, symptoms, or the clinical sequelae of a suspected overdose of either study drug or a concomitant medication. For this study, report all overdose events within 24 hours of awareness by the study site, using the Overdose eCRF, whether or not the overdose is associated with an AE.

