5.2. Demographic and Baseline Characteristics

All demographic and baseline characteristic data will be summarized by treatment group using descriptive statistics for all IBS subjects, IBS-D and IBS-M based on the FAS. In addition, the summary will be prepared for PPS-D.

The summary table will include age, age category ((<40 , ≥ 40 to <65 , ≥ 65 years), sex, child bearing potential (Yes/No), ethnicity, race, baseline abdominal pain intensity score (<6 vs ≥ 6), baseline IBS subtype (IBS-D vs. IBS-M) (only for all IBS subjects), previous IBS diet (Yes/No), category of previous IBS diet if Yes, baseline hypertension category (Hypertension vs. normotensive), pre-existing hypertension (Yes/No), weight, height and BMI.

Baseline Hypertension will be defined as baseline systolic blood pressure (SBP) ≥ 140 mmHg or baseline diastolic blood pressure (DBP) ≥ 90 mmHg, regardless of medical history.

Pre-existing hypertension will be defined as having a medical history of hypertension or baseline hypertension (baseline SBP ≥ 140 mmHg or baseline DBP ≥ 90 mmHg). The following list of preferred terms will be used to search for medical history of hypertension:

- Accelerated hypertension
- Diastolic hypertension
- Essential hypertension
- Hypertension
- Hypertensive crisis
- Hypertensive emergency
- Hypertensive heart disease
- Malignant hypertension
- Malignant hypertensive heart disease

- Secondary hypertension
- Supine hypertension
- Systolic hypertension

Age (years), height (cm), weight (kg), and BMI captured at Screening will be summarized as a continuous variable.

All demographic data will be listed.

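### Tables 14.3.2.15 and 14.3.2.16 may undercount hypertension TEAEs, because they are selected with a 12-term medical-history list that has no raised-blood-pressure term

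*SAP*

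**What the plan says.** SAP 5.2 introduces the list for one purpose: "The following list of preferred terms will be used to search for medical history of hypertension". It has 12 entries, from accelerated hypertension to systolic hypertension.

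SAP 7.3 then applies it to on-treatment events: "Hypertension TEAEs will be selected using the same list of preferred terms as specified in" Section 5.2. The programming notes in SAP 11.1.1 for Table 14.3.2.15 (by pre-existing hypertension) and Table 14.3.2.16 (by baseline hypertension status) write it out again: "Search for the following terms hypertension PTs: Accelerated hypertension, Diastolic hypertension, Essential hypertension, Hypertension, Hypertensive crisis", and so on to the same twelfth term. No other selection rule is given for these tables.

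The subgroups in the same tables do use readings. SAP 5.2 says "Baseline Hypertension will be defined as baseline systolic blood pressure (SBP) ≥ 140 mmHg" or diastolic pressure of at least 90 mmHg, whatever the medical history. Pre-existing hypertension is a history of hypertension or those same readings.

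In the protocol, hypertension belongs to the risks introduced in Section 2.3.2 with "AEs of special interest (AESIs) predefined for specific evaluations in vibegron clinical studies are as follows". Section 10.3 (Appendix 3) includes among reportable events abnormal laboratory results "or other safety assessments (eg, ECGs, radiological scans, vital signs measurements), including those that worsen from baseline, considered clinically significant" by the investigator.

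**The concern.** A term list for medical history looks for established diagnoses. A list for on-treatment events also has to find a rise that the investigator judged important enough to report but did not label as hypertension. The SAP uses the first list for the second job.

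Hypertension is an AESI for this drug, and these are the only visible adverse event tables that split it by hypertension status. If some reported rises are coded as findings, these tables would show fewer subjects with an event than were reported. A reader asking whether events arise mainly in women with or without prior hypertension would then be working from an incomplete count.

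**Working it through.** The plan states no figure on this point, so there is none to reproduce. The check compares the passages.

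**1. The list.** SAP 5.2 has 12 terms. The notes to Tables 14.3.2.15 and 14.3.2.16 have 12 terms. The two lists are identical. Terms containing *pressure*, *increas* or *elevat*: 0 of 12. All 12 name hypertension or hypertensive disease.

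**2. Can an event fall outside the list?** Two rules in Protocol Section 10.3 act together:
- A vital-sign worsening is an adverse event if the investigator judges it clinically significant.
- A diagnosis is to be recorded in place of signs and symptoms whenever possible.

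The second rule moves entries towards the listed terms. It does not remove the case where a rise is judged significant but no diagnosis is made. Under usual MedDRA coding (an assumption), that event takes a term such as *blood pressure increased*, which is not on the list.

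**3. Rows against columns.** Take a hypothetical woman with no history of hypertension and a baseline of 138/88 mmHg. She is in the No column of both tables. On treatment she reaches 150/95, and the site reports a clinically significant raised reading. The tables count no hypertension event for her, although 150/95 at baseline would have put her in the Yes column of both.

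**4. Size.** Let *s* be the share of subjects with a blood-pressure adverse event whose only such event is coded as a finding. Then

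share counted in the two tables = 1 − *s*

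| *s* (assumed) | share counted |
|---|---|
| 0% | 100% |
| 25% | 75% |
| 50% | 50% |
| 75% | 25% |

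If *s* is equal in both arms, the risk difference shrinks by the same factor and the risk ratio does not change. The documents give neither *s* nor an event rate, so the table shows only how the rule behaves.

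**5. Where else such an event would appear.**

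| Output | Stated to use the 12 terms? | Split by hypertension status? |
|---|---|---|
| Tables 14.3.2.15, 14.3.2.16 | yes | yes |
| All TEAEs by SOC and PT (14.3.2.2) | no | no |
| Overall TEAE table with AESI categories (14.3.2.1) | no | not stated |
| AESI tables and listing (14.3.2.12, 14.3.2.13, 14.3.2.21) | no | not stated |
| Blood pressure change of at least 5/10/15 (SAP 7.5) | not applicable (readings) | yes |

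The gap is therefore confined to the first row.

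**The case against.** The case for leaving the plan alone is substantial.

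- **Recording rule.** Protocol Section 10.3 prefers diagnoses and requires clinical significance, so many relevant events should reach a listed term. This stands. It means the undercount is possible, not certain, and may be small.
- **Other outputs.** Any raised-blood-pressure TEAE still appears by arm in the all-TEAE table, and in the AESI outputs if it is flagged there. This stands, and it confines the problem to two tables. Those outputs do not supply a pooled count of subjects by hypertension status.
- **Measured blood pressure.** SAP 7.5 counts subjects with a change of at least 5/10/15 at three consecutive visits and at Week 12, by pre-existing and by baseline hypertension, independently of adverse event coding. This largely stands. The analysis uses change rather than a hypertension threshold, and it drops a subgroup that makes up less than 25% of the population.
- **No testing.** SAP 7 plans no inferential tests on safety data, so no formal conclusion depends on these tables. This stands.

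A reader might go further and infer that the plan understates hypertension risk as a whole. The documents do not support that, for the reasons in the second and third items. A reader might also infer that the loss falls mainly on previously normotensive women, because a known hypertensive already has a diagnosis to enter. That is plausible, but nothing in the documents describes how sites record such events in either group.

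**Conclusion.** The concern holds in a limited form. The stated rule cannot count an adverse event coded as raised blood pressure, and the protocol allows such events to be reported. Tables 14.3.2.15 and 14.3.2.16 may therefore undercount hypertension TEAEs. The amount is unknown and could be zero.

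This rests on one assumption from outside the documents: that such entries are coded, as is usual in MedDRA, to terms other than the 12.

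A reader might also infer that the hypertension AESI counts are too low, or will disagree with these two tables. Neither can be shown. The protocol's definition of the hypertension AESI (Section 8.4.7) is blacked out, and the SAP does not state how those events are identified or that the 12 terms apply to them.

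This is a worthwhile correction to two descriptive tables. It does not affect the efficacy analysis.

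**What to change.** Before unblinding, change the selection rule in SAP 7.3 and in the notes to Tables 14.3.2.15 and 14.3.2.16. Select as hypertension TEAEs:

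1. the 12 existing terms;
2. the raised-blood-pressure preferred terms of the MedDRA version in use (for example blood pressure increased, and the systolic and diastolic equivalents);
3. any TEAE flagged to the hypertension AESI category.

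Show the result by preferred term, so that diagnoses and findings can be read separately. State in the same place how hypertension AESIs are identified. Leave the SAP 5.2 list as it is, for medical history only.

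The cost is a short text change and a longer search list, with no new data. SAP 7.3 already plans to finalize and document its gastrointestinal/IBS term list before database lock, so the step fits existing practice. The downside is that some transient readings will enter the tables; the display by preferred term makes them visible.
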